2.9 Early termination of the study

The Sponsor-Investigator may terminate the study prematurely according to certain circumstances, as follows:

- ethical concerns,
- insufficient participant recruitment,
- when the safety of the participants is doubtful or at risk, respectively,
- alterations in accepted clinical practice that make the continuation of a clinical trial unwise

2.10 Protocol amendments

All study staff are allowed to provide suggestions for a protocol amendment. But the PI is the only one

who is allowed to amend the protocol. Substantial amendments are only implemented after approval of the CEC.

Under emergency circumstances, deviations from the protocol to protect the rights, safety and wellbeing of human subjects may proceed without prior approval of the CEC. Such deviations will be documented and reported to the CEC as soon as possible.

All non-substantial amendments are communicated to the CEC within the Annual Safety Report (ASR).

3. BACKGROUND AND RATIONALE

3.1 Background and Rationale

Functional dyspepsia (FD) with postprandial distress is a common functional gastrointestinal (GI) disorder characterized by the occurrence of epigastric symptoms such as early satiety (fullness), nausea and upper abdominal pain after meals at least twice a week over at least six months (Rome IV criteria).(1) By definition, no structural disease is found on routine laboratory, endoscopy or imaging studies. Instead, symptoms are thought to be related to abnormal gastrointestinal motility (e.g. impaired gastric relaxation, abnormal emptying) and increased sensitivity to gastric distension and the digestive process.(2) Additionally, detailed studies of the mucosa often reveal low-grade inflammation in the duodenum and hyperpermeability ("leaky gut").(3)

Epidemiological studies report a 10-30% prevalence of functional dyspepsia (FD).(4) When dyspeptic symptoms are short in duration and relatively mild, many patients wish to self-manage with dietary adaptation and /or over the counter (OTC) preparations.(5) Others report high rates of intolerance to prescription medications.(5, 6) In these patients complementary and alternative medicines (CAM) based on natural products, such as plant-based "phytotherapy", are particularly appealing.(7) Several herbal therapies for functional dyspepsia have been tested in randomized clinical studies.(8) These include phytochemicals such as peppermint oil that inhibits smooth muscle contraction by direct blockade of calcium channels and other effects, deglycyrrhizinated licorice that increases gastric mucus secretion and may enhance mucosal protection and other preparations that combine multiple herbal products with the intention of inducing synergistic effects that promote normal digestive function.(9) In particular, STW-5 (Iberogast[©], Bayer) has been shown to have physiological effects on gastric accommodation and contractility. A double-blind non-inferiority randomized control trial (RCT) comparing Iberogast to cisapride (5-HT4 agonist) showed equal effectiveness for both medications,(10) and a meta-analysis of 3 double blind RCTs provided evidence that Iberogast is more effective than placebo in the treatment of dyspeptic symptoms.(11)

Amara Drops (Weleda, Arlesheim, Switzerland) is a proprietary preparation used for many decades in anthroposophic medicine that is marketed for the treatment of functional digestive disorders. Patients take 10-20 drops before meals to relieve loss of appetite, bloating, nausea, and other dyspeptic symptoms. These bitter substances are thought to promote digestion and relieve symptoms by stimulating the secretion of gastric and pancreatic enzymes, upper gastrointestinal motility and gastric emptying. These prokinetic effects may be therapeutic in patients with functional dyspepsia because there is an association between delayed gastric emptying (GE) and upper gastrointestinal symptoms including uncomfortable fullness, nausea and vomiting.(2, 12, 13) To date, the effects of Amara has not been subjected to pre-clinical or clinical studies.

The primary aim of this investigator-initiated, prospective, open-label, therapeutic study is to test if Amara has effects on the perceived severity of abdominal symptoms in patients with functional dyspepsia. Additionally, the physiological effects of Amara on gastric motor and sensory function will be assessed using validated methods

To test this, a prospective, open label, non-randomized study will assess (i) Perceived effects of regular intake of 10-20 Amara Drops prior to main meals on dyspeptic symptoms using the validated Leuven Dyspepsia Questionnaire. (ii) Physiological effects of 20 drops Amara tincture on gastric emptying using the 400ml Nottingham Test Meal with non-radioactive ¹³C-acetate breath test and concurrent assessment of filling sensation and dyspeptic symptoms by Visual Analogue Scores (VAS). (iii) In a subset of 20 consecutive patients, gastric electrical activity before, during and after ingestion of the test meal will be measured using the non-invasive Gastric Alimetry System (high-resolution gastric mapping / electro-gastrography) with concurrent heart rate monitoring. Gastric Alimetry is a diagnostic test for patients with chronic gastric symptoms, a development of electrogastrography that maps gastric

neuromuscular activity using a large array of electrodes over the abdomen. The test can help differentiate if patients have gastric neuromuscular dysfunction, gastric sensory disorder, gastric outlet obstruction or a functional (central) cause of symptoms. Individuals that fulfill the diagnostic criteria for functional dyspepsia with postprandial distress syndrome according to the Rome IV criteria will be recruited. At the first study visit (Study visit #1), Symptom questionnaires and other questionnaires to assess general health and psychiatric well-being will be completed at the time of recruitment. To answer the questions, the study participants are sent a one-time link to the questionnaires. Additionally, a Lüscher Color Test (LCT) will be performed. This non-verbal, non-written test has been developed to assess patient's personality and psychiatric state. This could be of interest in patients with disorders of brain-gut interaction that may not admit to the role of central factors in their illness.

Eligible patients will have no clinically relevant medical co-morbidity or previous gastrointestinal surgery and must have had a normal upper gastrointestinal pan-endoscopy in the previous 3 years. If not known, Helicobacter pylori status will be assessed by ¹³C-stool antigen test (repeat endoscopy not required). The first visit is followed by a 2–4-week run-in period. The presence and severity of dyspeptic symptoms will be reported using an on-line application downloaded on the patient's smart phone (an electronic reminder will be sent at 21:00 every day).

The LCT will be repeated during the second study visit (Study visit #2). At this time, gastric function will be assessed by ¹³C-breath test measurements with concurrent assessment of visceral sensitivity.

Amara Drops will be dispensed with 10-20 drops (0.25-0.50ml) taken three times a day before meals for 4 weeks. The patients are free to vary the dose within these parameters as considered appropriate. The amount taken will be monitored by checking the volume remaining in the bottle at the end of the 4-week intervention. During this time, patients will continue entering their symptoms and any side effects into the app.

At the end of the study period (Study Visit #3) the questionnaires, the LCT and the ¹³C-breath test measurement with concurrent assessment of visceral sensitivity will be repeated. An e-mail with the questionnaire link will be send to the patient shortly before the third study visit. Additionally, the patients will be asked if their global satisfaction was better on Amara treatment, whether they wish to continue treatment and /or recommend the treatment to others with similar symptoms.

3.2 Investigational Product (treatment) and Indication

Composition of the investigational medicinal product (IMP): The herbal preparation is manufactured by Weleda AG, Arlesheim. Besides the bitter substances Artemisia absinthium, Cichorium intybus, Juniperus and Gentiana lutea, Amara Drops contain also Centaurium, Peucedanum, Achillea millefolia, Salvia officinalis and Taraxacum, all nine plant substances held in an alcohol-based tincture.

The full indication text licensed by Swissmedic is: "According to the anthroposophical knowledge of man and nature, Weleda Amara-Drops can be used for digestive complaints such as heartburn, flatulence and bloating after meals, to stimulate the bile flow and for loss of appetite and nausea. The effect of Weleda Amara drops is based on a balanced mixture of medicinal plants with tonic (invigorating) and aromatic bitter substances, which are suitable for stimulating digestion. Weleda Amara drops mildly stimulate the secretion of saliva and gastric juices, promote the formation and secretion of bile and thus facilitate the digestion of fats. In addition, they are effective against flatulence and cramps."

3.5 Dose Rationale

Patients will take 3 x 10-20 drops of Amara before meals daily for four weeks (see section 8.1). The standard dose of this preparation is 10-15 drops before meals to "stimulate the digestive process"; however, patients are encouraged to adapt the dose to their requirements. Patient compliance will be assessed using a smart phone application that will record whether medication was taken and the severity of symptoms at the end of each day. Patient compliance (i.e. actual intake) will be checked by weighing the bottle at the end of the treatment period.

A 2-4-week run-in period between screening and the start of treatment is applied to ensure that the severity of symptoms is representative (patients tend to present during periods with relatively severe symptoms, thus run-in periods reduce the influence of spontaneous "regression to the mean" providing false positive results). The treatment period of 4-weeks is in accordance with the above-mentioned studies for other aromatic bitter substances and represents the minimum recommendation for study duration in functional gastrointestinal disorders.(15)

3.6 Explanation for choice of comparator (or placebo)

No comparator will be used in this study.

3.7 Risks / Benefits

The initial assessment of patients with functional dyspepsia will adhere to international guidelines on the investigation of this condition. It is widely recognized that current pharmacological treatment for dyspepsia is sub-optimal and new options are to be welcomed.

Amara Drops (Weleda) is a proprietary preparation that has been marketed over the counter (OTC) for many years. No serious side effects have been reported. Health status can improve thanks to the treatment used in this study, fewer dyspeptic symptoms could be possible and by participating in the trial, the results can also benefit future patients. However, we cannot guarantee that there will be a benefit from participating in this trial.

There are no expected risks associated with participating in this study. Very rarely, hypersensitivity or intolerance reactions may occur, this could include skin rash or gastrointestinal symptoms. Weleda AG analysed the safety profile of Amara. A pharmacovigilance monitoring between 2006 and 2021 showed very few reports of adverse drug reactions (see section 3.5).

Gastric emptying studies are recommended in patients with functional dyspepsia that do not respond to first-line, dietary management and empirical treatment.(16) Unlike standard investigation of gastric emptying by scintigraphy, the ¹³C-breath test is not radioactive and is suitable for repeated measurements.(17) The 400ml (300kcal) Nottingham Test Meal is based on a proprietary liquid nutrient drink (Fresubin, Energy Drink) often provided to patients with gastrointestinal and other diseases that require supplementary enteral nutrition. It is not associated with adverse outcomes. Clinical validation studies report that intake of the 400ml NTM is tolerated by all healthy controls and >95% of patients with functional dyspepsia without inducing vomiting.(18, 19)

3.8 Justification of choice of study population

Study participants will be recruited from patients referred to Gastroenterologists at Clinic Arlesheim for

assessment of dyspeptic symptoms. Investigations in this patient group identify an organic cause of these persistent symptoms in less than 1 in 4 cases.(16) Instead, functional dyspepsia is considered to be a disorder of brain-gut interaction, with symptoms related to both abnormal gastric motor function (e.g. delayed gastric emptying) and sensory function (peripheral hypersensitivity but also abnormal central processing).(1) Conservative measures (e.g. reduction in dietary fat) and medical treatment (e.g. acid suppression, prokinetics) often fail to improve symptoms.(5) Moreover, concerns about long-term side effects for certain medications (e.g. domperidone, metoclopramide),(20) and high rates of intolerance to prescription medications are reported.(5, 9) For these reasons, there is a clinical need for new and effective treatments of functional dyspepsia. Complementary and alternative medicines (CAM) based on natural products, such as plant-based "phytotherapy", are particularly appealing.(7, 9)

There are no previous studies that have assessed the effect of Amara Drops in functional dyspepsia. Before randomized double blind controlled studies can be considered prospective, open-label therapeutic study to assess perceived changes in symptom burden will be performed (at the same time the feasibility of recruiting this patient group and performing gastric emptying and other studies will be assessed). In this prospective open label study, placebo effects are likely to be present. Previous randomized controlled trials of therapy in functional gastrointestinal disorders indicate that this can be up to 40% in this group.(15) To compensate for this confounding factor and to demonstrate convincing changes in perceived symptom burden at least 60% of patients should show improvement on-treatment compared to off-treatment (run-in phase). Assuming a moderate effect (Cohen's effect size of 0.4) on the primary outcome measure (effect size and standard deviation as in a previous paper by Carbone et al. (21)) power calculation suggests that 58 patients are required to detect a significant effect at a convincing level of statistical significance (beta 0.9, alpha <0.01).

Any patients unwilling to participate in the study will not be included the study and will receive appropriate investigation and management that may include ¹³C breath test assessment of gastric emptying and Amara drops.

Furthermore, we guarantee that a physician not participating in the study, safeguards participant interest and insures proper medical care ([name], Medical Director Internal Medicine, Specialist in Internal Medicine and Gastroenterology at Clinic Arlesheim).

4. STUDY OBJECTIVES

4.1 Overall Objective

The purpose of the present study is to evaluate whether the herbal drug Amara improves the subjective, perceived burden of abdominal symptoms in patients with functional dyspepsia. It will also assess if the treatment is well tolerated. The present study will also investigate psychological and physiological function. This additional information should provide insight into which patients benefit the most from the treatment with Amara. The results of this prospective, open-label therapeutic study will also inform the study design for any subsequent RCT study in functional dyspepsia.

4.2 **Primary Objective**

Document perceived changes in upper gastrointestinal, dyspeptic symptoms reported by patients with functional dyspepsia treated with Amara for 4 weeks, as assessed by the Leuven Dyspepsia Score between visit 1 (off treatment) and 3 (after treatment)..

4.3 Secondary Objectives

Assess perceived effect of Amara on other gastrointestinal symptoms using validated, patient related outcome measurements (reflux disease questionnaire, IBS Symptom Severity Score).

Assess effect of Amara on (i) visceral sensitivity and (ii) gastric emptying (¹³C-breath test) in patients with functional dyspepsia with validated 400ml Liquid Nottingham Test Meal. Repeat testing will also allow an assessment of reproducibility to be obtained (iii) In a subset of 20 consecutive patients, gastric electrical activity will be measured using the non-invasive Gastric Alimetry System (high-resolution gastric mapping / electro-gastrography) with concurrent heart rate monitoring.

Participants will be asked also to rate their overall satisfaction with Amara and the number that request an additional prescription of Amara for the period after the study will be documented, as an indication of perceived effectiveness.

Additionally, factors that predict the outcome of Amara treatment in functional dyspepsia will be assessed. These factors will include (i) age (ii) sex (iii) severity of dyspeptic symptoms (iv) presence of other gastrointestinal symptoms (v) presence of psychological comorbidity (vi) presence of heightened visceral sensitivity after ingestion of the NTM (vii) abnormal gastric emptying during ¹³C gastric emptying test (viii) compliance with study procedures.

Additionally, the Lüscher Colour Test will be acquired. This non-verbal, non-written test was developed to provide insights into personality and psychological state. This could be of interest in patients with disorders of brain-gut interaction that may not admit to the role of central factors in their illness. Reproducibility of LCT will be documented by repeating the test at Study visit #1 and #2. Correlation with dyspeptic symptoms, psychological or physiological state will be assessed.

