ШΤ	Investigator-initiated Trial
KLA	Klinik Arlesheim
LCT	Lüscher Colour Test
LDQ	Leuven Dyspepsia Questionnaire
NTM	Nottingham Test Meal
OTC	Over The Counter
PHQ-12	Patient Health Questionnaire 12-items, depression module
PI	Principal Investigator
RCT	Randomised Controlled Trial
RDQ	Reflux Disease Questionnaire
SAE	Serious Adverse Event
SDV	Source Data Verification
SOP	Standard Operating Procedure
SPC	Summary of product characteristics
SUSAR	Suspected Unexpected Serious Adverse Reaction
TMF	Trial Master File

STUDY SCHEDULE

Study Periods	Screening	Physiological Measurement and Treatment	Physiological Measurement and End
Visit	1	2	3
Time (days)	Ca14-28d	1	28±14d
Medical History and Demographics	x		
Leuven Dyspepsia Questionnaire (LDQ)	x		x
Screening questionnaires	x		
Pregnancy test (urine)	x	(x)	
In-/Exclusion Criteria	x		
Patient Information and Informed Consent	x		
Primary Outcome Measure: LDQ total score	x		x
Secondary Outcome Measure: other GI symptom questionnaires	x	x	x
Lüscher Colour Test	x	x	x
Physiological Measurement (13C BT, HRV)		x	x
Intake of the Study Medication (Amara Drops)		x	x
Compliance with therapy			x
Satisfaction with therapy / Whether a prescription of Amara is wanted			x
Concomitant Medication, Therapy	x	x	x
Serious Adverse Events	x	x	x

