An appointment will be made 2-4-weeks later for the second study visit at which time the ¹³C gastric emptying study will be performed again. The run-in period is 2-4-weeks. This reduces the influence of spontaneous "regression to the mean" (i.e., false positive results).(15)

Gastric motor and sensory function will be assessed by ingestion of the 400ml, 300kcal Nottingham Test Meal (NTM) labelled with ¹³C acetate. This provides both an assessment of patient symptoms / visceral sensitivity to gastric filling with the 400ml liquid nutrient meal and also an assessment of gastric emptying. The 400ml NTM can be ingested by >95% of patients with functional dyspepsia.(19,

24) The ¹³C isotope is not radioactive, it takes 2-hours to complete and this technique is very appropriate for repeated assessment of gastric emptying.(16) In a subset of 20 consecutive patients, gastric electrical activity will be measured before, during and after ingestion of the Nottingham Test Meal using the non-invasive Gastric Alimetry System (high-resolution gastric mapping / electro-gastrography). Concurrent heart rate monitoring will provide an assessment of cardiovagal tone / autonomic nervous function.

The treatment period with Amara drops is four weeks per patient; participants will be instructed to take 10-20 drops of the herbal medicine Amara three times a day before meals over 28 days. This treatment period is in accordance with previous studies for aromatic bitter substances and represents the minimum recommendation for study duration in functional gastrointestinal disorders.(15) During the treatment period patients will record their symptoms using a mobile application (reminder will be sent at 21:00 every day). In addition, patients can note side effects that they perceive to be caused by Amara. If participants do not regularly provide this information, then a team member will call to ask if they have any problems.

At the end of the treatment period the participant will return to Clinic Arlesheim for repeat assessment. The LDQ and other patient related outcomes will be assessed again and ¹³C gastric emptying study will be repeated on treatment.

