At the end of the study, all participants will return the supply of Amara. The study team will assess compliance by counting the empty bottles and weighing partly used bottles. Patients will be asked whether they wish to continue the medication (yes / no). If the response is positive, then ongoing treatment will be recommended. Amara is classified by Swissmedic as dispensing category D available following discussion with specialist without prescription ("Abgabekategorie D: «Abgabe nach Fachgespräch»).

Overall, approximately 30 minutes will be needed to complete the questionnaires on each occasion. The total time required per patient during the study is a maximum of 8 hours (reading documents, filling in questionnaires, gastric emptying study (twice)).

During the period the participants are enrolled in this study no additional outpatient examinations are planned. If, while someone is participating in the study, acute symptom occur and the need arises for early outpatient assessment or inpatient admission to the clinic, the study would be terminated for this subject as of this date.

Limitations:

- The study will provide a prospective assessment of perceived treatment effectiveness; however, a large non-specific (placebo) effect is likely to be present as in any open-label, single-arm study in patients with functional gastrointestinal disease. This limitation is factored into the power calculation which requires at least a moderate treatment effect for Amara to be considered effective. Note that the secondary analysis that will identify baseline factors (e.g., age, sex, symptom severity, gastric emptying rate) that associate with treatment effect will be relatively less sensitive to this confounding factor.

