- In addition to subjective patient related outcome measures, repeat ¹³C breath testing with the Nottingham Test Meal on and off treatment will provide physiological assessment of effects of Amara on gastric motor and sensory function. Continuous assessment of patient sensations during Drink tests (i.e., gastric filling) may be less impacted by patient recall than questionnaires. ¹³C breath testing provides an indirect assessment gastric emptying based on the excretion of ¹³CO₂ in the expired air. Although well validated against scintigraphy, it remains uncertain to what extent these results can be affected by individual patient factors other than gastric emptying (e.g. metabolism). Note that this limitation will not affect the results of this study because we will compare gastric emptying in patients on and off Amara treatment (i.e., patients act as their own control).
- Amara drops will be distributed for self-administration at home, thus, we rely on participants to report their intake accurately. Compliance will be checked as described above.
- The four-week duration of drug intake is relatively brief and may underestimate the treatment effect.
- This study may suffer from the limitation that participants will take other over the counter medications or engage in other treatments at home.
- This study design does not allow evaluating the efficacy of Amara medication. However, the aim of this prospective study is to acquire results on overall effectiveness that will inform the design of a randomized controlled study with this aim.

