9.3.2 Study visits

On the second visit, patients will complete a combined assessment of gastric motor and sensory function off treatment with the Nottingham Test Meal, with gastric emptying documented by ¹³C-Breath Testing. On completion of the test, the test substance will be provided to the patient with instructions on how and when to take the Amara. An appointment will be made 4-6 weeks after this appointment for the third and final visit. Based on this, the start day for the intervention will also be determined.

During the 4-week intervention, 10-20 drops of Amara will be taken prior to every meal. Patients will document their symptoms every day using a mobile application. Adverse events can also be recorded. Paper forms are available if required. A reminder will be sent to complete this electronic form every day at 21:00.

Shortly before the third study visit participants receive an e-mail with a questionnaire link. All questionnaires will be completed again. If it is noted during the visit that the questionnaires has not been filled in, this can be done in the waiting room or during the visit. The patient will complete a combined assessment of gastric motor and sensory function on Amara treatment with the Nottingham Test Meal, with gastric emptying documented by ¹³C-Breath Testing. On completion of the test, in addition to the PROM, the patient will be asked about their subjective assessment of the intervention, whether ongoing treatment is desired and whether they would recommend the treatment to other patients with functional dyspepsia. Additionally, compliance with study procedures will be assessed (bottle(s) of Amara will be weighed). At the end of the study, patients are reimbursed a lump sum of 50 Swiss francs for expenses (gas, parking fee, train ticket etc.). More can be provided if an invoice supported by receipts is sent to the principal investigator.

In a subset of 20 consecutive patients, gastric electrical activity will be measured before, during and after ingestion of the Nottingham Test Meal on the second and third study visit using the non-invasive Gastric Alimetry System (high-resolution gastric mapping / electro-gastrography). Concurrent heart rate monitoring will provide an assessment of cardiovagal tone / autonomic nervous function.

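### Section 4.3 promises breath-test reproducibility, but the scheduled tests are one off and one on Amara, which gives only an upper bound on repeatability error; the protocol also disagrees on whether an earlier off-treatment test is done

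*Protocol*

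**What the plan says.** Section 4.3 lists the effect of Amara on visceral sensitivity and gastric emptying as a secondary objective, then adds "Repeat testing will also allow an assessment of reproducibility to be obtained". It does not say which two tests are to be compared. For the Lüscher Colour Test, the same section does name the pair: visits 1 and 2, both before Amara is started.

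Most of the protocol describes two breath tests per patient:

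- In the Study Schedule, the row "Physiological Measurement (13C BT, HRV") is marked at visits 2 and 3, and the visit 1 cell is empty.
- Section 9.3.1 lists no breath test among the screening procedures.
- Section 9.3.2 places the visit 2 test before the drops are handed out ("gastric motor and sensory function off treatment with the Nottingham Test Meal") and the visit 3 test during treatment ("gastric motor and sensory function on Amara treatment with the Nottingham Test Meal").
- Section 3.1 describes breath tests at visits 2 and 3 only.
- Section 6.1, in its estimate of patient time, counts "gastric emptying study (twice").

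Two places point the other way. The Protocol Summary in the synopsis mentions breath testing with sensitivity measurement immediately before it says that the run-in follows visit 1, and then describes the visit 2 test separately. Section 6.1 says that at visit 2 the "gastric emptying study will be performed again".

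**The concern.** Reproducibility is the agreement between repeated measurements under the same conditions. On the schedule, the only repeat is made after treatment has started, and the limitations in section 6.1 assign that same comparison to the drug effect: repeat testing "with the Nottingham Test Meal on and off treatment will provide physiological assessment of effects of Amara". The visit 2 to visit 3 difference in one patient contains that patient's response to Amara, any change over time, and measurement error. With one difference per patient, these cannot be told apart.

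If the spread of these differences were published as the repeatability of the test, it would make the test look noisier than it is wherever patients respond differently. The protocol gives reasons to expect unequal responses: patients choose between 10 and 20 drops (section 8.3), section 8.4 allows for intake below half of that prescribed, and section 4.3 looks for factors that predict outcome. Section 4.1 says the results will inform a later randomised trial, where an inflated error SD could mislead planning.

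The contradiction on the number of tests also matters in itself. A reader of the synopsis and a reader of the schedule would arrive at different visit 1 procedures.

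**Working it through.** **Step 1: count the tests.** The protocol's own figure is two gastric emptying studies per patient. Schedule and section 9.3: visit 1 = 0, visit 2 = 1 (off), visit 3 = 1 (on). Total 0 + 1 + 1 = 2, so the stated count is reproduced. Adding the test implied by the synopsis and by the wording for visit 2 in section 6.1 gives 3, of which two are off treatment.

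**Step 2: what an off/on pair estimates.** Write the difference for patient i as

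D_i = δ + t_i + e_i2 − e_i1,

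where δ is the mean change on Amara, t_i is the patient's deviation from that mean (SD τ), and each error e has SD s, the true within-patient SD. Take t_i as independent of the errors, and s as the same off and on treatment. The usual within-patient SD from pairs then targets

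- mean change left in: √(s² + (δ² + τ²)/2)
- mean change removed: √(s² + τ²/2)

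Removing the mean takes out δ, including any shift common to all patients over time. It does not take out τ.

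**Step 3: size.** The protocol gives no value for δ, τ or s, so τ is assumed over a range. With the mean removed and s = 1:

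- τ = 0.5: √(1 + 0.25/2) = √1.125 = 1.06
- τ = 1: √(1 + 1/2) = √1.5 = 1.22
- τ = 2: √(1 + 4/2) = √3 = 1.73
- τ = 0 (nil or uniform effect): 1.00, no inflation

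The same effect on an intraclass correlation with an assumed true value of 0.80 (between-patient variance 4, error variance 1, t_i also independent of the patient's level): the off/on value is 2 × 4 / (5 + 5 + τ²) = 8 / (10 + τ²), or 0.78, 0.73 and 0.57 for τ = 0.5, 1 and 2.

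**Step 4: what an off/off pair would give.** With visits 1 and 2 both before Amara, δ and τ drop out and the estimate targets s over the run-in interval. With 60 pairs (the completer target in section 7.4, 59 degrees of freedom), its 95% confidence limits are √(59/χ²) at the 97.5% and 2.5% points of chi-square, about 0.85 and 1.22 times the estimate. That precision would be adequate, so the obstacle is which pair is measured, not the number of patients.

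**The case against.** Several arguments on the other side have force.

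- *The aim may be achievable.* If the visit 1 test implied by the synopsis and section 6.1 is done, visits 1 and 2 form exactly the pair required. A reader might infer from the schedule that reproducibility cannot be assessed at all; the documents do not establish that, because they contradict each other. The weight favours two tests: the schedule, both parts of section 9.3, section 3.1 and the count in section 6.1 agree, and the synopsis text is damaged at this point and sits in a paragraph about eligibility. The reproducibility sentence still needs a pair that the schedule contains.
- *An off/on pair is not worthless.* After mean adjustment it bounds repeatability error from above, and under the Step 2 model it is right if Amara has a nil or uniform effect. This stands.
- *One set of pairs can serve two summaries.* A reader might think it inconsistent to report both a drug effect and a variability measure from the same differences. It is not: the mean and the spread are different quantities. The fault is only in labelling the spread as reproducibility.
- *The inflation rests on assumptions.* It does. At τ = 0.5 it is 6%, which is small. A larger figure such as 1.41 (δ = τ = s) needs an analyst who leaves the mean change in, and the protocol does not plan that.
- *It is a side remark.* Breath-test reproducibility is not listed as an outcome in sections 5.2 or 5.3, section 11 calls all secondary outcomes exploratory, and section 5.2 refers to an appendix procedure that is not shown. This limits the importance but does not correct the sentence.

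**Conclusion.** The point holds in a limited form. On the schedule and visit procedures, section 4.3 claims a property that the design does not have: one off and one on measurement yield an upper bound on repeatability error, not repeatability itself. With the mean change removed, the overstatement of the within-patient SD runs from about 1.06 to 1.73 times for τ between 0.5 and 2 times s, and is nil if the effect is nil or uniform. The size is therefore unknown, and only the direction is known. That direction rests on the response being independent of measurement error and on error variance being equal off and on treatment.

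Alongside this, the protocol contradicts itself on whether an off-treatment breath test takes place at visit 1. How that is resolved decides whether the reproducibility statement can stay.

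Severity is low. The aim is exploratory, and neither the primary LDQ comparison nor the average on/off comparison of gastric emptying is affected by this point.

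**What to change.** First reconcile the Protocol Summary in the synopsis, the Study Schedule, and sections 4.3, 6.1 and 9.3 on how many breath tests each patient has and at which visits. Then:

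- **If only visits 2 and 3 are tested:** remove the reproducibility statement from section 4.3, or restate it as an upper bound on measurement variability computed after removing the mean change. Report visit 2 to visit 3 as within-patient change. Correct the synopsis text and the section 6.1 wording that presents the visit 2 test as a repeat.
- **If an off-treatment test is in fact done at visit 1:** enter it in the Study Schedule and section 9.3.1, correct the count and time estimate in section 6.1, and state in section 4.3 that reproducibility is taken from visits 1 and 2, as that section already does for the Lüscher Colour Test.

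The first route costs wording only, and one side objective may be given up. The second adds nothing if the test is already being done; if it is not, it means a further test of about 2 hours per patient (the duration given in section 6.1), which this exploratory aim alone does not clearly justify.
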